7.2 Formulation

7.2.1 LAT8881 capsules

Each capsule contains 30 mg LAT8881 plus [REDACTED] excipients.

7.2.2 Placebo capsules

Placebo capsules contain the excipients [REDACTED] only (without LAT8881).

7.3 Manufacturer

LAT8881 is manufactured [REDACTED] in accordance with current Good Manufacturing Practice (cGMP).

The active and placebo blends for encapsulation is formulated and the capsules are filled [REDACTED] under cGMP conditions.

[REDACTED] is responsible for quality control and stability testing.

7.4 Storage

At the study site, the IMP must be stored refrigerated (2-8°C) in a secure area, with access limited to authorised personnel.

Subjects will also be asked to store their treatment at home under refrigeration.

7.5 Packaging and labelling

IMP capsules will be packaged in bottles [REDACTED]. Each bottle will contain 2 IMP capsules (2 capsules of formulated LAT8881 or 2 placebo capsules). The two bottles for treatment of each subject (active/placebo) will be packaged together in a clear plastic bag, according to the randomisation schedule prepared by the unblinded study statistician. Each bottle will appear identical to the other bottle in the box, except for the treatment period number (1/2 or 2/2) on the label.

Bottles containing the IMP capsules and the bag in which they are packed will be labelled according to Annex 13 of the PIC/S Guide to Good Manufacturing Practice.¹⁵

Each bottle will have both a permanently attached label and a tear-off drug accountability label. The tear-off accountability label must be removed and attached to the Drug Accountability log when the product is dispensed. On dispensing, a dispensing label will be attached permanently to the bottle.

Details of labelling and dispensing will be provided in the Study procedures manual.

7.6 Randomisation and blinding

A computer-generated randomisation schedule and treatment allocation will be prepared by an unblinded statistician prior to the start of the study.

The treatment sequence each subject will receive will not be disclosed to the investigator, study site personnel, subjects, or sponsor personnel. The randomisation codes will be available to the Investigator if required for emergency unblinding purposes (see Section 8.1).

7.7 Dispensing of investigational product

The investigator is responsible for ensuring that IMP is dispensed in accordance with the protocol and only to subjects enrolled in the study.

On the morning of Day 1, after receipt of a prescription/authorisation from the investigator (or delegate), the study nurse (or Investigator) will obtain the allocated treatment. The subject's study number, date and treatment number will be recorded in the Drug accountability log. The log will be countersigned by the investigator and must be available for inspection at any time.

7.8 Method for assigning subject study number

At screening, each subject will, in chronological order, be allocated a unique Screening number (Subject ID).

At randomisation on Day 1, the subject will be assigned a unique Randomisation number, which will be allocated in ascending order according to their chronological order of inclusion in the study. Confirmation of the randomisation number allocated to each subject will be documented in the drug accountability records and recorded in the CRF.

The Subject ID number will be used to identify the subject throughout the study and on all study-related documentation.

7.9 Accountability of study supplies

All supplies of IMP are provided for use only in this clinical study and must not be used for any other purpose.

The investigator or designee is responsible for accountability of IMP, reconciliation and record maintenance. The investigator or designated site staff must maintain accountability records throughout the course of the study including prescriptions for IMP, records of the amount of IMP dispensed, the identification of the subject to whom the IMP was dispensed, the date and the amount dispensed.

Subjects must bring their medication bottles with them to clinic visits at the end of each treatment period and the number of remaining capsules will be entered onto the CRF. The product, including used bottles and records, must be available for inspection by a study monitor during the study.

Following completion of the study, remaining unused supplies will be returned to Lateral or destroyed as directed by the sponsor.

7.10 Doses and treatment regimens

Subjects will be instructed to take one dose of IMP (two capsules) with water within one hour of the onset of a migraine headache of moderate to severe intensity.

7.11 Dose reduction/dose adjustments

No within-subject dose reductions or adjustments are permitted. If a subject experiences an adverse event requiring (in the investigator's opinion) temporary or permanent suspension of the IMP, the subject should be withdrawn from the study (refer to Section 5.7).

8. Treatment compliance

Subjects will be asked to return their IMP bottles for a capsule count at each end of treatment period visit.

Study drug accountability forms will be kept by pharmacy during the study and will be reviewed by the study monitor. Treatment compliance will be recorded in the subject's source documents and the CRF.

8.1 Unblinding

8.1.1 Medical emergency

In a medical emergency, when management of a subject's condition requires knowledge of the study drug, the code may be broken to determine the treatment allocation of the subject. Details will be provided in the Study manual.

Wherever possible, such emergencies should be discussed with the study medical monitor and/or sponsor before breaking the code and disclosure of the treatment allocation (or as soon as possible thereafter). The date, reason for and name of the individual breaking the code will be documented along with a list of unblinded persons.

8.1.2 End of study

The randomisation schedule, allowing identification of the treatment sequence received by each subject, will be disclosed after approval and locking of the database.

8.2 Concomitant medications and treatments

8.2.1 Prohibited medications

Medications for migraine prophylaxis are prohibited:

- from 6 months prior to Screening and throughout the study:
 - Calcitonin gene-related peptide pathway monoclonal antibodies CGRP antagonists, eg erenumab (Aimovig)
- from 3 months prior to Screening and throughout the study
 - Antiepileptic drugs including valproate, topiramate
 - Betablockers
 - Triptans (eg naratriptan for premenstrual migraine)
 - Tricyclic antidepressants (TCAs)
 - Botulinum toxin
 - Calcium channel blockers
 - MAO-A inhibitors
 - Nerve blocks
 - Serotonin-norepinephrine (noradrenaline) reuptake inhibitor: eg venlafaxine, duloxetine
 - Selective serotonin reuptake inhibitors, eg fluoxetine, sertraline
- from Screening and throughout the study
 - NSAIDs
- Investigational drugs for prophylaxis or treatment of migraine or other medical conditions

Any other medications which may impact on pain assessments are prohibited if taken within 24 hours prior to taking the dose of IMP.

8.2.2 Prohibited treatments

The following treatments are prohibited during the study, including during the screening period:

- Neuromodulation devices, including TENS, eTENS, vagus nerve stimulation devices and acupuncture

8.2.3 Permitted medications

The following medications are permitted:

- 1 Rescue analgesics, 2 or more hours after dose of IMP: prescription and nonprescription drugs including Standard of Care medications for treatment of acute migraine headache
- 2 Other medications eg vitamins, herbal/dietary supplements (including Chinese medicines), oral and IUD contraceptives, hormone replacement therapy, not on the prohibited medications list which have been stable for 3 months prior to screening.

Subjects who change concomitant medication during the study period should notify the investigator promptly and details of the medications used should be documented in the source documents and CRF. Concomitant medications will be recorded by both the generic and the Trade name.

9. Study procedures

The Schedule of Assessments for the study are provided in Section 2.

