6.2 Exclusion criteria

Subjects who meet any of the following criteria will be excluded from the study:

1. Unable to distinguish migraine from other primary headache conditions
2. Average of 15 or more headache (migraine or nonmigraine) days per month or history of more than 25% of headaches occurring at time of wakening (wake up headaches)
3. History of aura lasting more than 60 minutes
4. History of vomiting within 2 hours of onset of a migraine headache in more than 25% of migraine headaches
5. Medication overuse headache, defined as:
 - a. use of opioids, triptans or ergot alkaloids or any combination of these medications for treatment of headaches 10 or more days per month during the 90 days prior to screening OR
 - b. Non-steroidal anti-inflammatory drugs (NSAIDs) or simple analgesics for treatment of headaches on more than 14 days per month during the 90 days prior to screening
6. Recent (3 years) history of frequent or chronic hemiplegic/ basilar migraine, tension headache, retinal migraine, ophthalmoplegic migraine as per ICHD classification, or treatment resistant atypical migraine

7. Hospital admission for status migrainosis or medication overuse headache within 6 months of screening
8. Current clinically significant systemic disease or neurological or psychiatric condition which in the opinion of the investigator or sponsor could jeopardise the safety of the subject or the validity of the study results
9. Cerebrovascular disease, including but not limited to a history of stroke or recent (3 years) transient ischaemic attack (TIA)
10. Major surgery within 6 weeks of screening or planned during the study period
11. Clinically significant abnormality as assessed by the investigator or sponsor's medical monitor on haematology, biochemistry, vital signs, physical examination or 12-lead electrocardiogram (ECG)
12. Malignancy within 5 years of screening, with the exception of carcinoma *in situ*, non-melanoma skin cancers and prostate cancer not requiring treatment or on stable (> 6 months) treatment with hormone therapy
13. History of alcohol abuse, illicit or illegal drug use in the last 2 years
14. Use of Prohibited medications or treatments within the specified time period before Screening or planned during the study
15. Participation in another clinical trial or administration of any investigational product or experimental product within 60 days or 5 half-lives (whichever is longer)

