## 9.2 Per Protocol (PP) Population

The Per Protocol (PP) population will include all subjects who received at least one dose of IMP and excludes subjects who have any major protocol deviation impacting the study endpoints. Deviations

for exclusion from the PP population due to inadequate exposure to IMP or completeness of primary efficacy endpoint will be determined during the blinded review meeting prior to database lock.

*A per-protocol (PP) population will be used for efficacy analyses and to analyse exploratory endpoints.*

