### **11.6 Prior and Concomitant Medications**

Medications will be summarised by the study periods below:

- Prior or Pre-Day 1 (Visit 2)
- Pre-IMP: irrespective of the study periods
- Post IMP: LAT8881 60 mg and Placebo

The number and percentage of subjects who have taken any prior medication and number of mentions will be summarised by treatment sequence. Medications will be classified by Therapeutic Main group (ATC Level 2) and Chemical Subgroup (ATC Level 4). The therapeutic main group and chemical substance group will be displayed in the descending order of frequency of total number of mentions. Medications will be coded using the World Health Organisation's Drug-Dictionary (WHODD) version September 2019 or later.

Percentages will be based on the safety population.

The summary will also be presented for concomitant medications by treatment overall and within each study period separately.

Treatment overall: Medications reported before any IMP, irrespective of the study periods will be summarised as 'Pre-IMP'. Medications reported after IMP in period 1 and before IMP in period 2 will be summarised under the treatment assigned at period 1. Medications reported after IMP in period 2 will be summarised under the treatment assigned at period 2. Medications that are ongoing from the previous period and new events will be summarised separately within each treatment period and treatment.

By Study Period: Medications reported post-IMP within each period and treatment will be summarised under the corresponding treatment for that period. Medications that are ongoing from the previous period and new events will be summarised separately within each treatment period and treatment. If a subject has ongoing medication in more than one study period, then the use of that medication is counted in all applicable study periods as 'ongoing'.

Rescue medications and other non-rescue medications will be presented separately. Rescue medications will be presented first followed by other non-rescue medications within the same table.

Percentages will be based on the safety population.

In DDP: Table 14.1.6.1, Table 14.1.6.2 and 14.1.6.3

Prior and Concomitant medications will be listed by subject and therapeutic subgroup. Use of prohibited medications will be recorded as protocol deviations and will be listed in 16.2.2.1.

Rescue medication use over the treatment periods will be listed for each subject separately.

In DDP: Listing 16.2.4.4 and Listing 16.2.4.5

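### Protocol 8.2.1 and 8.2.3 leave open whether NSAID rescue is prohibited, and under the SAP that open question can decide who stays in the primary per-protocol population

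*Protocol*

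**What the plan says.** **Protocol.** Section 8.2.3, item 1, permits "Rescue analgesics, 2 or more hours after dose of IMP: prescription and nonprescription drugs including Standard of Care medications". No class is excepted, and only item 2 (other stable medications) refers back to the prohibited list.

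Section 8.2.1 opens with "Medications for migraine prophylaxis are prohibited". Under that lead-in, triptans are barred from three months before screening, with naratriptan for premenstrual migraine as the example. NSAIDs have their own window, "from Screening and throughout the study", with no example and no rescue exception. The list closes: "Any other medications which may impact on pain assessments are prohibited if taken within 24 hours prior to taking the dose of IMP". The synopsis repeats both lists.

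Exclusion 14 rules out "Use of Prohibited medications or treatments within the specified time period before Screening or planned during the study". Section 9.2 has subjects score screening attacks before and after their usual migraine drug, in the window in which NSAIDs are listed as prohibited.

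**SAP.** Section 11.6 states: "Use of prohibited medications will be recorded as protocol deviations". Section 11.2 splits deviations into major and minor without a grading rule. Under section 9.2 the PP population "excludes subjects who have any major protocol deviation impacting the study endpoints", and membership is settled at the blind review. Protocol 14.5 makes PP primary for efficacy and also promises all results on the full analysis set (FAS). SAP 11.8.1.3 fits the mixed model on PP only, and SAP 11.8 leaves descriptive FAS summaries to the blind review meeting.

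**The concern.** The same NSAID tablet taken three hours after the study dose can be read as permitted rescue or as use of a prohibited drug. On the second reading it is a deviation. An analgesic taken before the 4, 8 and 24 hour scores can plausibly be judged to affect the endpoints.

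If that deviation is graded major, the whole subject leaves PP. That discards the scores recorded before the rescue and the subject's other treated attack. Subjects take rescue because relief was poor, so the exclusion depends on the outcome and is likelier after the less effective treatment. Two things are at stake: the size of a primary set built on 20 planned completers, and a treatment comparison and pain-free rates estimated after some treatment failures have been removed.

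**Working it through.** **1. The plan's own figure.** Twenty completers with up to 20% non-completion: 20 / (1 − 0.20) = 25. The plan enrols 26, and 26 × 0.80 = 20.8, so the figure holds. This point does not change it.

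**2. The two lists side by side.**

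| Evidence | Points towards |
|---|---|
| Lead-in to 8.2.1 refers to prophylaxis | Ban on prophylactic use only |
| Protocol 9.3 and 9.4 speak of routine prophylactics that are not on the prohibited list | List is one of prophylactics |
| Triptan example is prophylactic; exclusion 5a tolerates acute triptan use below 10 days a month in the 90 days before screening, inside the triptan window | Prophylaxis only, for triptans |
| NSAIDs have their own window, no example and no rescue exception | Unclear |
| Closing sentence gives other pain-affecting drugs a 24-hour pre-dose window, as if listed drugs were barred outright | Ban by drug |
| 8.2.3 item 1 excludes no class; Protocol 3.1 cites guidance naming NSAIDs for acute attacks | NSAID rescue permitted |
| 9.2 has usual migraine medication taken during screening | Acute use expected |

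Exclusion 5b does not settle the NSAID question. It concerns the 90 days before screening, and the NSAID window starts at screening.

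**3. Route out of PP.** Prohibited use → deviation (SAP 11.6) → graded major or minor (SAP 11.2, no rule) → if major and affecting endpoints, the subject is excluded (SAP 9.2). Each step is possible; none after the first is prescribed.

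**4. Possible loss from PP.** The documents give no rescue rate and no NSAID share, so every input here is assumed. Let rL and rP be the rescue rates on LAT8881 and placebo, and s the share of rescues treated as prohibited-drug use. Assume each such use is graded major and the two periods are independent. Then

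PP completers = 20 × (1 − rL·s) × (1 − rP·s)

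| rL / rP | s = 25% | s = 50% | s = 75% |
|---|---|---|---|
| 30% / 50% | 16.2 | 12.8 | 9.7 |
| 50% / 70% | 14.4 | 9.8 | 5.9 |

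For example, 20 × (1 − 0.15) × (1 − 0.25) = 12.75. If the SD of the paired differences were unchanged, falling from 20 to 12.75 subjects would widen the standard error by √(20/12.75) = 1.25.

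**5. Possible bias (simulations on assumed inputs).**

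- *Rescue when relief at 2 h is under 1 point.* Mean 2 h change is −1.5 on placebo and −2.5 on LAT8881, between-subject SD 1.2, residual SD 2. Rescue rates come out at 42% and 26%. If each rescued attack carries a 50% chance of exclusion, the paired difference moves from −1.00 to −0.89 and 70% of subjects stay. If every rescued subject is excluded, it moves to −0.57 and 46% stay. With no true effect it stays at 0.
- *Rescue probability rising with 2 h pain.* True difference −0.95 after scale limits, SD 2.5, within-subject correlation 0.4, rescue in 56% of placebo and 44% of LAT8881 attacks. With s = 25%, 50% and 75%, 23%, 43% and 59% of subjects leave PP and the difference becomes −0.94, −0.91 and −0.83. The largest shift is 0.12. The standard error of the paired mean at n = 20 is 2.5 × √(2 × (1 − 0.4)) / √20 = 0.61, so that shift is about one fifth of a standard error.

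**The case against.** The strongest reply is that the lists do not conflict: the prohibited list concerns prophylaxis and rescue is acute treatment. A reader might infer a flat contradiction covering NSAIDs and triptans alike. The documents do not support that. For triptans the prophylactic example and exclusion 5a favour a ban on prophylactic use only. The entry on investigational drugs mentions treatment as well as prophylaxis, but this cuts both ways, since the authors added treatment where they meant it. For NSAIDs the reply does not settle the matter, because nothing in the entry or in 8.2.3 says which reading applies.

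The second reply is procedural. Exclusion needs a major grade at a blinded review, rescue is tabulated separately in SAP 11.6, and the synopsis names one site, so disagreement between sites is not the issue. This stands in part: exclusion is possible, not prescribed. But blinding hides allocation, not poor response.

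Third, FAS summaries could expose a large loss, since SAP 11.8 bases that decision on the difference in numbers between the populations. They remain optional and descriptive.

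Finally, a reader might extend the point to rescue before 2 hours. That breaches an unambiguous timing rule, and keeping those attacks in PP is a separate, debatable choice.

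**Conclusion.** The point holds as an ambiguity about NSAIDs that can reach the primary analysis. The protocol does not say whether NSAID rescue is prohibited, and the SAP does not say whether it would cost a subject PP membership.

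The size rests wholly on assumed rescue rates, class shares and grading. Over the ranges tabulated, 4 to 14 of 20 completers would leave PP (20 − 16.2 = 3.8; 20 − 5.9 = 14.1), from a modest loss to more than half. A reader might infer that PP would be emptied, but even the harshest case tabulated keeps about 6. In the partial-exclusion scenarios a true effect is attenuated by at most 0.12 points. The larger shift of 0.43 requires every rescued subject to be excluded. No bias appeared in the simulation with no true effect. The more certain harm is lost precision and a primary set whose membership depends on an unresolved reading.

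The rescue endpoint in Protocol 10.4 has no class restriction, so its definition is not affected.

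**What to change.** **Protocol.** Reconcile 8.2.1, 8.2.3, exclusion 14 and the synopsis copies, so that each listed class states whether the ban covers prophylactic use only or also acute use after the study dose. Check that 9.2 agrees with the result. Which rule applies is for the sponsor's clinicians; this review takes no position.

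**SAP 9.2, before the blind review.** Add:

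*Rescue medication taken after the IMP dose as permitted by protocol section 8.2.3 is an outcome, is not a prohibited-medication deviation, and is not a ground for exclusion from PP.*

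The sentence follows 8.2.3 as reconciled. If the clarified ban reaches acute use of a class, the SAP should also state in advance how such use is graded.

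**Cost.** One protocol clarification and one SAP sentence, with no change to the planned 20 completers or 26 enrolled. The downside is that PP keeps subjects whose later scores are affected by rescue. They remain identifiable from the separate rescue listing in SAP 11.6.

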9.1 Subject informed consent

Following identification of potential subjects, staff in the clinic will contact the subject, explain the nature of the study and confirm potential interest and eligibility. The Participant (Subject) information sheet (PIS) and Consent forms (ICFs) may be provided. The subject will then be invited to attend the clinic for further information, signing of the ICF and conduct of screening procedures.

The investigator must provide adequate information regarding the study, including its purpose, possible risks and potential benefits. Subjects must also be advised that they are free to discontinue from the study at any time. Subjects must be given time to review the study information and ask any questions.

Written informed consent must be provided by the subject before any tests or investigations outlined in the study protocol are carried out.

The ICF must be personally signed and dated by both the investigator and the subject. The investigator must store the original, signed ICF with the subject's medical notes/source documents. A copy of the signed and dated ICF will be given to the subject.

Screening procedures may commence immediately following signing of the ICF.

